# Calculations

Intraoperative ventilation variables collected in the parent studies included tidal volume  $(V_T)$ , positive end–expiratory pressure (PEEP), plateau or maximum airway pressure (Pplat or Pmax) and respiratory rate (RR).

Ventilation parameters are calculated as follows:

For  $V_T$ , expressed in ml/kg predicted body weight:

50 kg + 2.3 kg (height in inches -60) (in males)

45.5 kg + 2.3 Kg (height in inches -60) (in females)

For driving pressure ( $\Delta P$ ):

 $\Delta P = Pplat - PEEP$  (with volume–controlled ventilation [VCV])

 $\Delta P = Pmax - PEEP$  (with pressure-controlled ventilation [PCV]) [11] For mechanical power of ventilation (MP):

MP = 0.098 \* VT \* RR\* (Ppeak – 0.5 \* ΔP) (with VCV) [12]

MP = 0.098 \* VT \* RR \* (Pmax – 0.5 \* ΔP) (with PCV) [13]

For respiratory system compliance (CRS):

$$C_{RS} = V_T / \Delta P$$

# Sample size

The sample size will be based on the number of available patients.

# Statistical analysis plan

Demographic, clinical and outcome variables are presented as medians with interquartile ranges (IQR), or number with percentage, where appropriate. Differences in baseline characteristics between patients with and patients without hypocapnia will be analyzed using the Pearson Chi–squared or Fisher exact tests for categorical variables and with a one–way ANOVA or Kruskal–Wallis test for continuous variables.

Data points for intraoperative variables (vital signs, ventilator settings and ventilation parameters) will include those collected in the first, second and third hour after start of the study, and before extubation.

Occurrence of postoperative pulmonary complications will be compared using a Fisher's exact test, time to event analyses will be performed using a Cox proportional hazard model or a competing risk model where appropriate. Next, we will perform a propensity matched cohort. Patients will be matched 1:1 with a maximum caliper of 0.02. The following covariates will be used for propensity matching: age, gender, BMI, type of surgery, compliance, history of COPD. We will calculate interaction term for the ARISCAT score as sensitivity analysis. We will perform time-weighted analysis for etCO2 levels in the primary end-points. Kaplan-Meier curve will be used to plot the relation between hypocapnia and the primary outcome.

A LOESS regression will be used to visualize the relationship of etCO2 as a continuous variable with the primary outcome. The association between etCO2 and the primary outcome will be determined using a generalized mixed model in which age, gender, BMI, type of surgery, compliance and history of COPD will be used as covariates. Sankey plot will be used to demonstrate flow association between etCO2 and primary or secondary outcomes.

As a sensitivity analysis the main analyses will be repeated in obese patients and non-obese patients, using a cutoff of 30 kg/m^2 for BMI. Another sensitivity analysis will be performed to determine the effect of PEEP settings on outcome. For this analysis the interaction term for PEEP on the generalized mixed model will be calculated.

A P–value of < 0.05 will be considered statistically significant. All analyses will be performed with R statistics version 4.0.4.

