#### Hypothesis

Intraoperative hypocapnia has an independent association with patient demographics, ventilation parameters, and perioperative complications.

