### Study design

For this analysis we will use the database of the two randomized clinical trials, named the 'High versus Low Positive End–expiratory Pressure During General Anesthesia for Open Abdominal Surgery (PROVHILO) [3], and the 'PRotective Ventilation with Higher versus Lower PEEP during General Anesthesia for Surgery in OBESE Patients' (PROBESE) [9]. PROVHILO and PROBESE investigated the effects of an open lung approach during low tidal volume ventilation in patients undergoing major surgery.

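### Two trials with different populations are pooled, but trial is in neither covariate list and no analysis of the primary outcome is stratified by trial

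*Combined protocol and SAP*

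**What the plan says.** All references are to the combined protocol and SAP.

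- **Study design:** "For this analysis we will use the database of the two randomized clinical trials". The title of one trial places it "During General Anesthesia for Open Abdominal Surgery", that of the other "during General Anesthesia for Surgery in OBESE Patients". The Rationale calls the work an individual patient-level meta-analysis.
- **Hypothesis:** "Intraoperative hypocapnia has an independent association with patient demographics, ventilation parameters, and perioperative complications".
- **Statistical analysis plan, unadjusted comparison:** "Occurrence of postoperative pulmonary complications will be compared using a Fisher's exact test". No stratification is mentioned.
- **Statistical analysis plan, matching:** "The following covariates will be used for propensity matching: age, gender, BMI, type of surgery, compliance, history of COPD". Matching is 1:1 with a caliper of 0.02, and there is no requirement to match within trial.
- **Statistical analysis plan, model:** a "generalized mixed model in which age, gender, BMI, type of surgery, compliance and history of COPD will be used as covariates". No random effect is named.
- **Statistical analysis plan, time to event:** a Cox or competing-risk model, with no terms listed.
- **Nearest items to a by-trial analysis:** a repeat of the main analyses above and below a BMI of 30 kg/m², and a descriptive table of patient characteristics by study (eTable 1, under Planned inserts).

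**The concern.** Hypocapnia was not randomized, so the comparison is observational and trial can confound it. Trial may carry differences in centres, period, protocol and the recording of complications. The Study outcomes section takes the composite as the parent studies used it, so any difference in ascertainment would follow trial. Whether the trials differ in these respects is not stated.

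BMI and type of surgery overlap with trial but do not determine it, since an obese patient having open abdominal surgery could come from either trial. A between-trial difference that the six covariates do not explain, and that affects both hypocapnia and complications, would be read as an effect of hypocapnia. It could act in either direction. At stake is the word independent in the hypothesis.

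**Working it through.** **Is there a figure to reproduce?** No. The Sample size section refers only to the patients available, and no rates are given. Every number below rests on assumed inputs with no true effect of hypocapnia within either trial.

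**Step 1. Unadjusted comparison, by arithmetic.** Let w be the first trial's share of patients, h1 and h2 the hypocapnia proportions, and r1 and r2 the complication risks.

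- Pooled risk with hypocapnia = [w·h1·r1 + (1−w)·h2·r2] / [w·h1 + (1−w)·h2]
- Pooled risk without = [w(1−h1)r1 + (1−w)(1−h2)r2] / [w(1−h1) + (1−w)(1−h2)]

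With w = 0.5 the weights cancel:

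- *10-point gaps (hypocapnia 70% v 60%, complications 35% v 25%).* With: (0.245 + 0.150)/1.3 = 0.304. Without: (0.105 + 0.100)/0.7 = 0.293. Odds ratio (OR) 1.05.
- *20-point gaps (70% v 50%, 40% v 20%).* With: (0.28 + 0.10)/1.2 = 0.317. Without: (0.12 + 0.10)/0.8 = 0.275. OR 1.22, or 1.20 if w = 0.3.
- *20-point gaps in opposite directions (70% v 50%, 20% v 40%).* With: (0.14 + 0.20)/1.2 = 0.283. Without: (0.06 + 0.20)/0.8 = 0.325. OR 0.82.
- *Either rate equal across trials.* The two pooled risks coincide. OR 1.00.

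For N = 2000 and a normal approximation to the Fisher test, the chance of a significant result in the direction of the bias (nominal 2.5%) is 6–7% in the first case and 41–51% in the second.

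**Step 2. After the planned adjustment, by simulation.** Assumed: hypocapnia about 60%, complications about 30%, and N of 2400 split 1:2 or 1500 split 1:1. BMI was N(26, 4) v N(43, 6) or N(27, 5) v N(38, 5), with the second trial truncated at 30. Type of surgery and compliance were either related to trial or not. COPD was 10% v 7%, and age and sex were equal. Gaps are the part that does not act through the six covariates. There were 1000 datasets per setting, so the Monte Carlo standard error is about 0.7 points at 5%.

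| Analysis | OR, 10-point gaps | False positives | OR, 20-point gaps | False positives |
|---|---|---|---|---|
| Planned matching | 1.00–1.02 | 4–7% | 1.01–1.07 | 4–11% |
| Six covariates, no trial term | 1.01–1.02 | 4–7% | 1.04–1.08 | 5–14% |

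Across all settings, adding trial to the model, matching within trial or a Mantel-Haenszel analysis by trial gives OR 0.99–1.02 and 4–7% false positives. With equal complication rates there was no bias. Under the planned matching, 5–28% of pairs crossed trials.

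**Step 3. The unnamed random effect.** At 20-point gaps (400 datasets per setting, standard error about 1.1 points, closer BMI setting only):

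- trial as random effect: OR 1.00–1.01, 3–7% false positives;
- centre as random effect: OR 1.04–1.07, 5–11%, removing about 5–36% of the bias in the log OR;
- centre as random effect plus a fixed trial term: OR 0.99–1.00, 2–7%.

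These runs used hypocapnia yes/no. The planned model uses etCO2, possibly as a continuous variable, so the figures are only a guide to that model.

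**Step 4. The BMI split.** Suppose the second trial admitted only patients with a BMI of 30 or more; its criteria are not in the documents. The non-obese stratum then comes from one trial, and at 20-point gaps the six-covariate model gives OR 0.97–1.01. The obese stratum still mixes both trials and gives OR 1.03–1.10.

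**The case against.** The strongest reply is that the harm is small. With 10-point gaps the planned adjusted analyses cannot be told apart from those that include trial. A visible excess needs 20-point gaps in both rates that bypass all six covariates, and nothing in the documents supports gaps of that size. The upper ends of the ranges are also maxima over many settings and include simulation noise. This stands, and it limits the severity.

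Four stronger readings are tempting, and the documents do not support them:

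- *The main analysis is badly biased because the Fisher test is unstratified.* The plan does not call that test primary. It is the first comparison listed, it omits every confounder by design, and adjusted analyses follow. The larger figures in Step 1 apply to it alone.
- *The mixed model ignores trial.* In an individual patient-level meta-analysis, study is a natural grouping factor, and a random effect for trial would deal with the problem in that model. The text does not settle it, so for that model the defect is missing detail and not a shown bias. The same holds for the unlisted Cox terms.
- *The random effect is the patient.* Data points for the intraoperative variables "will include those collected in the first, second and third hour after start of the study, and before extubation", which might suggest this. But the primary outcome is one composite per patient, so a patient intercept is barely workable for it.
- *A cross-trial pair is an error.* Propensity matching balances groups on average. Such pairs matter only if residual confounding by trial exists.

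What does not stand is the suggestion that existing safeguards suffice. BMI and type of surgery are partial proxies, the BMI split leaves the obese stratum mixed, and eTable 1 describes patients without adjusting anything.

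**Conclusion.** The point holds as a gap in the adjustment set, of minor to moderate severity. The plan pools two trials with different populations, gives a closed list of six covariates for both adjusted analyses, and leaves trial out of each. No analysis of the primary outcome is stratified by trial.

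The size cannot be derived from the documents. Under the stated assumptions, the bias after planned adjustment is negligible with 10-point residual gaps and modest with 20-point gaps (OR up to about 1.08). The unadjusted comparison is more exposed, at about 1.05 to 1.22 when the gaps run in the same direction. The bias vanishes if either rate is equal across trials. If the mixed model's random effect is trial, that model is essentially protected, but the matched and Fisher comparisons are not.

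**What to change.** In the Statistical analysis plan section:

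1. Match exactly within trial.
2. Enter trial as a fixed effect in the mixed model and name the random effect, for example centre within trial if an identifier exists. Two trials are too few to estimate a random-effect variance well, so a fixed term is the clearer choice.
3. Stratify any Cox or competing-risk model by trial.
4. Optionally, report a trial-stratified Mantel-Haenszel result beside the Fisher test.
5. Keep the BMI 30 strata, but not as a substitute for a trial term.

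The cost is a change of wording and one model term. Trial membership is already needed for eTable 1; the documents do not say whether a centre identifier is available. The downside is slightly fewer matched pairs: 0.1–2.8% in the simulation, for example 924 falling to 898 (26/924 = 2.8%).

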#### Study details

The full list of inclusion and exclusion criteria of PROVHILO and PROBESE have been reported with the original publications [3, 9]. In short, patients were eligible for participation in the original studies if: (1) planned for major (abdominal) surgery; and (2) at risk for postoperative pulmonary complications. Major exclusion criteria in the original studies were planned thoracic surgery or neurosurgery.

For the purpose of this current analysis, we will additionally exclude patients that underwent unscheduled, i.e., urgent or emergent surgeries, because we consider it likely that these patients may have had metabolic abnormalities at the moment of surgery, i.e., metabolic acidosis, for which the anesthesiologist may have adjusted the intraoperative ventilator settings. This may have led to a 'compensatory' low etCO2. We will also exclude patients for whom etCO2 recordings are missing in the study databases.

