#### Study outcomes

The primary outcome of this analysis is a composite of predefined and collected postoperative pulmonary complications within the first seven days after the surgery, as used in the parent studies. Postoperative pulmonary complications included mild, moderate, and severe respiratory failure; acute respiratory distress syndrome; bronchospasm; new pulmonary infiltrate; pulmonary infection; aspiration pneumonitis; pleural effusions; atelectasis; cardiopulmonary edema; and pneumothorax.

Secondary outcomes include intraoperative complications, a set of intraoperative ventilation parameters, intraoperative vital signs (heart rate, mean

3

arterial pressure, and SpO2) and any new arrhythmias needing intervention. Other endpoints are unexpected need for intensive care unit admission, ICU readmission, and length of stay in hospital up till day 90.

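### ARISCAT is not in the main adjustment sets, so baseline pulmonary risk not captured by the six listed covariates could bias the association claimed as independent

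*Combined protocol and SAP*

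**What the plan says.** All the relevant text on adjustment is in the section Statistical analysis plan.

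- For the propensity score: "The following covariates will be used for propensity matching: age, gender, BMI, type of surgery, compliance, history of COPD".
- For the association of etCO2 with the primary outcome: a "generalized mixed model in which age, gender, BMI, type of surgery, compliance and history of COPD will be used as covariates". These are the same six variables.
- ARISCAT has one mention: "We will calculate interaction term for the ARISCAT score as sensitivity analysis". The plan does not say which model receives the term, how the score is coded, or whether its main effect is included. It gives no reason for leaving the score out of the two adjustment sets.
- The first comparison of the primary outcome is unadjusted: "Occurrence of postoperative pulmonary complications will be compared using a Fisher's exact test". No covariates are named for the Cox or competing-risk model.

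Elsewhere, the section Hypothesis reads "Intraoperative hypocapnia has an independent association with patient demographics, ventilation parameters, and perioperative complications". The primary outcome, under Study outcomes, is "a composite of predefined and collected postoperative pulmonary complications within the first seven days after the surgery". Under Study details, patients could enter the parent trials if they were, among other things, "at risk for postoperative pulmonary complications", and for this analysis "we will additionally exclude patients that underwent unscheduled, i.e., urgent or emergent surgeries".

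**The concern.** The exposure is a classification made after the fact from recorded etCO2 (section Patient categories), so any claim of independence rests on what is adjusted for. The outcome is pulmonary complications. The plan already intends to compute with a risk score that it considers relevant to this association, yet it uses that score only to look for effect modification.

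Effect modification and confounding are separate questions. The interaction coefficient says whether the hypocapnia odds ratio changes along the score. The matched estimate and the mixed-model estimate are still produced without the score. If patients with higher baseline risk were also more (or less) often hypocapnic, beyond what the six covariates explain, that difference would appear in the main estimates as an association with hypocapnia.

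The plan itself accepts that patient condition can drive etCO2. It removes unscheduled surgery because metabolic state may have led the anesthesiologist to change the ventilator settings. The same logic makes baseline pulmonary risk worth controlling in the patients who remain.

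**Working it through.** **1. The text.** The documents give no number of patients, event rate, effect size or power, so there is no figure of the plan to reproduce. The two covariate lists agree item by item, and neither contains ARISCAT or any other overall pulmonary risk score. The textual part of the point is exact.

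**2. How large could the bias be?** Every input below is an assumption, and the true hypocapnia odds ratio is always 1. Let gE and gY be the log odds ratios, per SD of the risk not explained by the listed covariates, for hypocapnia and for complications. The hypocapnic group is then about gE SD higher in residual risk, and each SD adds gY to the log odds of complications:

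spurious log OR ≈ gE × gY.

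| Assumed residual OR per SD (hypocapnia; complications) | gE × gY | Approximate OR | Simulated OR, score omitted |
|---|---|---|---|
| 1.0; any | 0 | 1.00 | 1.00 |
| 1.05; 1.2 | 0.049 × 0.182 = 0.009 | 1.01 | 1.00 to 1.03 |
| 1.1; 1.3 | 0.095 × 0.262 = 0.025 | 1.03 | (same range) |
| 1.2; 1.5 | 0.182 × 0.405 = 0.074 | 1.08 | about 1.07 |
| 1.3; 2.0 | 0.262 × 0.693 = 0.182 | 1.20 | about 1.18 |

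The approximation runs slightly high in the last row.

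**3. False-positive rate.** Assume 30% complications and equal groups. Then SE(log OR) ≈ √[2 / (N/2 × 0.30 × 0.70)], which is 0.138 for N = 1000 and 0.098 for N = 2000.

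- OR 1.07, N = 1000: z = 0.068/0.138 = 0.49. P(Z > 1.47) + P(Z < −2.45) = 0.071 + 0.007, about 8%.
- OR 1.18, N = 2000: z = 0.166/0.098 = 1.70. P(Z > 0.26) is about 40%; simulations of this case gave 36% to 38%.
- The two weak settings in the table gave 4% to 6%, which is the nominal rate within simulation error.

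With the score in the model, the simulated odds ratio returns to about 1.00 and the rate to about 5%.

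**4. Dependence on overlap.** Now let the listed covariates explain a share s of the score's variance, with log odds per SD of the whole score of 0.3 for hypocapnia and 0.5 for complications, N = 2000, and 400 simulated datasets per setting. The formula becomes 0.3 × 0.5 × (1 − s).

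| s | Formula | OR, six covariates only | False positives | OR, score added | False positives |
|---|---|---|---|---|---|
| 30% | exp(0.105) = 1.11 | 1.10 | 18% | 1.00 | 5% |
| 60% | exp(0.060) = 1.06 | 1.07 | 12% | 1.01 | 8% |
| 90% | exp(0.015) = 1.02 | 1.02 | 6% | 1.01 | 5% |

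With 400 datasets, a rate of 5% has a standard error of √(0.05 × 0.95/400) = 1.1 points, so the 8% in the middle row lies above what chance would usually give. I repeated that setting with 4,000 datasets: 9% without the score and 5% with it. The 12% and 8% are therefore somewhat high by chance; the pattern does not change.

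**5. What the illustration is not.** These are plain logistic models with a binary exposure. They are not the planned 1:1 match or the mixed model of etCO2. They show direction and order of size only.

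**The case against.** The strongest reply has four parts.

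- *The interaction model would carry the main effect.* A properly specified interaction model normally includes ARISCAT as a main effect, so the sensitivity analysis would probably adjust for it. This stands against a stronger reading that a reader might infer, namely that the score is never handled as a confounder anywhere. The text leaves this open. It does not rescue the main estimates, because the matched cohort and the mixed model would still be fitted without the score.
- *The six covariates and the exclusion of unscheduled surgery may already capture most of the risk.* This stands as a limit on size. The documents do not list the components of ARISCAT, so the overlap cannot be measured from them, and at 90% overlap almost nothing remains. Equally, they give no evidence that the remainder is negligible.
- *No link between ARISCAT and hypocapnia is documented.* Correct. Another tempting inference is that patients were selected for risk and the groups must therefore differ in risk. That does not follow: restricting entry to patients at risk, if anything, narrows the spread of risk, and it says nothing about imbalance between hypocapnia groups. A spurious association is possible here, not demonstrated.
- *Matching may discard patients.* This can lower the false-positive rate. In the worst case above, with 70% of patients assumed hypocapnic, cutting to equal groups reduced it from 35% to 27%. The bias itself stayed at an odds ratio of about 1.18.

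The unadjusted Fisher test is a separate matter, and the change proposed here does not alter it.

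**Conclusion.** The point holds in a limited form. It is certain from the text that ARISCAT is outside both main adjustment sets and enters only through an interaction term in an unspecified sensitivity model. It is also certain that such a term does not control confounding in the main estimates.

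Whether this biases the result materially is not certain; my confidence on that is moderate. Under the assumptions shown, the spurious odds ratio lies between 1.00 and about 1.18, with false-positive rates from 5% to about 38%. The upper end needs residual odds ratios per SD of 1.3 for hypocapnia and 2.0 for complications at N = 2000. The lower end applies if residual risk is unrelated to hypocapnia or the listed covariates carry nearly all of the score. The documents do not show where in this range the study lies.

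I class it as an inexpensive improvement. It is not a demonstrated error in the result.

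**What to change.** In the section Statistical analysis plan:

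1. Add ARISCAT as a main effect to the propensity score and to the generalized mixed model. Either enter the whole score, or only those of its components not already among the six covariates. State which form is used, so that the same information is not entered twice.
2. Report the balance of ARISCAT between the matched groups.
3. Keep the interaction term as a separate effect-modification analysis. Name the model, state the coding of the score, and say that the main effect is included.
4. State how patients without a score are handled.

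The cost is a few lines of SAP text. No new data collection should be needed, since the plan already intends to analyse the score. The downsides are partial overlap with the listed covariates and possible loss or imputation of patients without a score. The documents do not report how complete the score is in either database, so that number should be checked before the form is chosen.

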#### **Patient categories**

We will use the intraoperatively collected  $etCO_2$  levels to classify patients as either 'with hypocapnia' or 'without hypercapnia', using the cutoff of 35 mmHg. A patient is considered 'hypocapnic' if the  $etCO_2$  was < 35 mm Hg at any point during surgery, from start of the study till end of the study, and classified as 'without hypocapnia' otherwise. In case of a missing value immediately before extubation, we will use the values as reported in the last hour of surgery [10].

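### Does leaving the etCO2 summary, its form and the random effect unstated make the mixed-model result for the primary outcome unreliable?

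*Combined protocol and SAP*

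**What the plan says.** The adjusted analysis rests on one sentence of the Statistical analysis plan: "The association between etCO2 and the primary outcome will be determined using a generalized mixed model", with age, sex, body mass index, kind of operation, compliance and prior COPD as covariates. The PEEP sensitivity analysis uses the same model: "the interaction term for PEEP on the generalized mixed model will be calculated".

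The exposure is measured repeatedly. Under Patient categories, a patient counts as hypocapnic if etCO2 "was < 35 mm Hg at any point during surgery, from start of the study till end of the study". If the value just before extubation is missing, "we will use the values as reported in the last hour of surgery". The Statistical analysis plan says that data points for intraoperative variables "will include those collected in the first, second and third hour after start of the study, and before extubation". That makes up to four time points, although etCO2 is not named in that sentence.

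The outcome is single. Under Study outcomes it is a "composite of predefined and collected postoperative pulmonary complications within the first seven days after the surgery".

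Two other sentences concern etCO2 as a quantity rather than a category. One reads "We will perform time-weighted analysis for etCO2 levels in the primary end-points", without a formula. The other begins "A LOESS regression will be used to visualize the relationship of" and treats etCO2 as continuous; it comes immediately before the mixed-model sentence.

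**The concern.** A mixed model is defined by its random effect, and none is named. With several readings per patient and one outcome, the term could suggest a long data set with one row per reading. Both obvious ways of running that fail. Without a patient term, each patient's outcome is counted up to four times and the standard error is too small. With a patient intercept, the outcome never varies within a patient, so the intercept variance has no finite estimate.

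One row per patient avoids both failures but leaves choices open: lowest, mean or time-weighted etCO2, and a straight line or a curve. A LOESS plot of the same relation is planned, so an analyst could pick the form after seeing the data. The Hypothesis section speaks of hypocapnia, whereas the model sentence speaks of etCO2, so the adjusted model might not address the exposure of interest. The PEEP interaction would inherit any fault.

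**Working it through.** The documents give no number of patients, event rate or variance for etCO2, so there is no figure of the plan's own to reproduce. Those inputs below are assumptions.

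**1. Readings as rows, no patient term.** With m readings per patient, intraclass correlation ICC for etCO2, and an outcome constant within patient, the variance is understated by the design effect DE = 1 + (m − 1) × ICC. The actual two-sided error at nominal 5% is 2 × [1 − Φ(1.96/√DE)].

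| m | ICC | DE | Actual error |
|---|---|---|---|
| 3 | 0.3 | 1.6 | 12.1% |
| 4 | 0.3 | 1.9 | 15.5% |
| 4 | 0.5 | 2.5 | 21.5% |
| 4 | 0.7 | 3.1 | 26.6% |
| 4 | 0.9 | 3.7 | 30.8% |
| 5 | 0.9 | 4.6 | 36.1% |

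A narrower assumption gives a figure inside this range. With total SD 4 mmHg and within-patient SD 2.5 or 1.5, ICC is 1 − 6.25/16 = 0.61 or 1 − 2.25/16 = 0.86. With four readings DE is 2.83 to 3.58 and the error about 24% to 30%. Nothing in the documents favours the narrower range.

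Simulation agrees. With four readings, 30% risk, adjustment for 20 centres and 600 runs per setting, the error was 23.3% (1000 patients) and 20.2% (2500) at ICC 0.5, and 24.2% and 27.8% at ICC 0.7. A centre effect alone does not protect this layout.

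**2. Readings as rows, patient intercept.** In one null data set of 500 patients, the fitted intercept SD was 5, 20, 86 and 400 when capped at 5, 20, 100 and 400. The etCO2 coefficient moved with it (−0.09, −0.03, −2.59, −2.58). In a separate null set of 600 patients the log-likelihood kept rising (−956, −474, −398, −362, −344 at SD 1, 5, 10, 20, 40). This is a failure to estimate, not a P-value shown to be too small.

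**3. One row per patient.** In the same runs as step 1's simulation, with centre indicators standing in for a random centre effect, the error was 4.5% to 7.2% using the mean and 4.0% to 6.7% using the lowest reading. The Monte Carlo standard error is √(0.05 × 0.95/600) = 0.9 points, so one setting is a little high and the rest are compatible with 5%. Separate null runs without centre effects gave 4.0% to 6.0% for single prespecified tests.

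**4. Which layout does the plan imply?**
- Study outcomes gives one outcome per patient.
- Five of the six covariates are single patient values; only compliance could vary over the operation.
- Study design pools two trials, and the References entry for one calls it multicentre. That is an ordinary reason for a mixed model with one row per patient.
- The model follows directly on a sentence treating etCO2 as continuous, and the only continuous patient-level summary the plan names is the time-weighted one.

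Nothing points the other way except the word mixed.

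**5. Choosing the summary after the fact.** Taking the smallest P-value raises the error to 7–8% over two forms of the mean, 11–13% over lowest or mean in two forms plus the indicator, and 12–18% over four summaries in two forms. These figures require selective picking, and the widest set includes first and last readings, which the plan never proposes as summaries.

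**The case for a change.** The strongest case for a change is that no sentence elsewhere supplies the missing items. The time-weighted analysis stands alone, without a formula or a stated link to the model; the word continuous is attached only to the LOESS plot; neither trial nor centre is named as a term. The row-by-reading layout is not excluded, its inflation is severe, and a few lines of text would rule it out. All of this is factually right, and the conditional arithmetic stands.

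What does not stand is the step from unstated to invalid. The failing layouts are ones the plan does not describe, and an analyst would see at once that a patient intercept cannot be estimated when the outcome is constant within patient. The risk of choosing the form from the LOESS plot is real in principle, but the plan gives that plot a descriptive purpose only.

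The mismatch with the hypothesis has an answer in the plan: the below-35 mmHg indicator is adjusted through the 1:1 propensity-matched cohort, on the same six covariates. The mixed model is naturally its continuous companion. Making the indicator the model's main exposure as well would be a preference. A power comparison in which the indicator is made the true exposure favours it by construction and cannot settle the matter.

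**Conclusion.** The omission is real, but it does not call for a change. The plan leaves unsaid the etCO2 summary, its form, the row unit and the random effect. On the ordinary reading, one row per patient with a trial or centre effect, the test holds close to its nominal 5% (4.0% to 7.2% in simulation). The 12% to 36% error belongs to a layout that the plan does not propose, and its size depends on assumed values of the intraclass correlation and the number of readings. The PEEP interaction is sound on the same reading. The conclusion rests on the analysts taking the patient as the unit, which the single outcome and the nearly all patient-level covariates support, and on not selecting the etCO2 summary or form by its P-value, which nothing in the plan suggests they will do.
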